6.7.18. The Change from Baseline in Glomerular Macrophage Count

Not applicable, given the Week 52 biopsy being optional.

6.7.19. The Change from Baseline in PGIC Score

The descriptive analysis described in Section 6.7.9 in the main SAP will be repeated at Week 52 based on the ITT Set by using available data through the Week 52 assessment.

Note per FDA guidance, PGIC should not be collected at baseline, and therefore should not be calculated/reported in the form of "change from baseline", this endpoint will be analyzed in a descriptive way of presenting the PGIC score at specific timepoint(s) only. This also applies to the analysis for the RCP period.

6.7.20. The Change from Baseline in EQ-5D-5L Score

The descriptive analysis described in Section 6.7.10 in the main SAP will be repeated at Week 52 based on the ITT Set by using available data through the Week 52 assessment.

Note that the individual component score of EQ-5D-5L will also be tabulated. This also applies to the analysis for the RCP period.

6.7.21. The Change from Baseline in WPAI Score

The descriptive analysis described in Section 6.7.11 in the main SAP will be repeated at Week 52 based on the ITT Set by using available data through the Week 52 assessment.

6.7.22. Change in Drusen from Baseline

The observed values for maximum drusen size (measured by total volume of drusen) and number of intermediate or large drusen will be summarized by treatment group and visit using ITT set. Summaries will present the descriptive statistics for baseline, absolute values, change and percentage change from baseline data by visit. Summaries will further be separated by left eye and right eye, respectively.

All maximum drusen size and number of intermediate or large drusen results will be listed for the ITT set.

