For participants with serum albumin levels below the LLN at baseline, the proportion of participants with normalization of serum albumin levels		X		
For participants with serum C3 levels below the LLN at baseline, the proportion of participants with serum C3 levels above the LLN		X		
The change from baseline in the FACIT-Fatigue Scale score		X		
The change from baseline in the KDQOL score		X		
The change from baseline in uPCR using the 24-hour urine collections	X^1	X^1		
The annual rate of change from up to 3 years prior to screening in eGFR	X	X		

Table 1: Efficacy Endpoints

Study endpoints	Week 26	Week 52		
The proportion of participants with reductions from baseline in proteinuria of at least 30%	X	X		
The proportion of participants with normalization of proteinuria	X	X		
The time to 50% reduction in uPCR with a stable or improved eGFR	n/a	n/a		
The time to normalization for the following parameters for participants in whom the parameter is abnormal at baseline: • serum C3 • uPCR • serum albumin • blood pressure	n/a	n/a		
The change in glomerular macrophage count, as determined by CD68 staining	X	X		
The change from baseline in PGIC score	X	X		
The change from baseline in EQ-5D-5L score	X	X		
The change from baseline in WPAI score	X	X		
Change in drusen from baseline:		X		

Abbreviations: C3G = C3 glomerulopathy; eGFR = estimated glomerular filtration rate; FACIT-Fatigue = Functional Assessment of Chronic Illness Therapy—Fatigue; KDQOL = Kidney Disease Quality of Life; LLN = lower limit of normal; PEG = polyethylene glycol; PGIC = Patient Global Impression of Change; uPCR = urine protein-to-creatinine ratio; WPAI = Work Productivity and Activity Impairment.

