10.6. Ophthalmologic Evaluation

Ophthalmologic evaluation is an optional assessment and will be performed at selected sites. If performed, participants should have a baseline ophthalmologic evaluation, including a basic ophthalmologic examination, spectral domain optical coherence tomography (SD-OCT), and color fundus photography, at an approved ophthalmologic clinical site at any time during the screening period. For those participants with drusen prior to pegcetacoplan administration, a followup- ophthalmologic evaluation, including a basic ophthalmologic examination, SD-OCT, and color fundus photography, is requested to occur at a convenient time between week 42 and week 52 of the study. The SD-OCT and color fundus photography will be acquired using a standardized protocol, performed by reading center certified imagers on registered equipment, and will be transmitted to a central reading center for evaluation. The basic ophthalmologic examination should include best-corrected visual acuity, intraocular pressure, and a dilated fundus examination with comment on presence or absence of pigment, drusen, hemorrhage, atrophy, or other evidence of macular degeneration.

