2.2.4. Exploratory Efficacy Endpoints

The primary, key secondary, and additional secondary efficacy endpoints will also be evaluated at week 52 as exploratory efficacy endpoints.

In addition, the following exploratory efficacy endpoints will be evaluated:

- The change from baseline in uPCR using the 24-hour urine collections at week 24 and week 48
- The annual rate of change from up to 3 years prior to screening in eGFR at week 26 and week 52
- The proportion of participants with reductions from baseline in proteinuria of at least 30% at week 26 and week 52
- The proportion of participants with normalization of proteinuria at week 26 and week 52
- The time to 50% reduction in uPCR with a stable or improved eGFR
- The time to normalization for the following parameters for participants in whom the parameter is abnormal at baseline:
 - serum C3
 - uPCR
 - serum albumin
 - blood pressure
- The change from baseline in glomerular macrophage count, as determined by CD68 staining at week 26 and week 52
- The change from baseline in Patient Global Impression of Change (PGIC) score at week 26 and week 52
- The change from baseline in 5-Level EuroQol-5 Dimension (EQ-5D-5L) score at week 26 and week 52

- The change from baseline in Work Productivity and Activity Impairment (WPAI) score at week 26 and week 52
- Change in drusen from baseline at week 52:
 - change in maximum drusen size
 - change in number of intermediate or large drusen

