1. INTRODUCTION

This statistical analysis plan (SAP) addendum provides a technical and detailed elaboration of the statistical analyses of efficacy and safety, supplementing what is described in the main SAP of the primary analysis (Week 26) and overall (combined with Week 26 SAP) clinical study report (CSR). The specified analyses to be performed as part of this SAP addendum do not supersede or replace any previously specified analyses, unless specified otherwise.

The specified analyses in this SAP addendum will serve the purposes of the planned analyses for the open-label period (OLP) reporting once all participants have completed the open-label treatment period or discontinued early and all corresponding data have been entered into the database, reviewed, cleaned, and finalized, and the database is locked.

The analyses of the OLP data associated with the primary CSR (dated 05 December 2024) were described in Version 1.0 of the SAP Addendum.

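### The addendum measures maximum drusen size by total drusen volume, which does not measure the largest druse and can change in the opposite direction

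*SAP*

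**What the plan says.** Main SAP Section 2.2.4 lists two drusen components at week 52: "change in maximum drusen size" and "change in number of intermediate or large drusen". Section 6.7 of the main SAP contains no drusen analysis.

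The operational text is in SAP Addendum version 2.0, Section 6.7.22. It summarises "The observed values for maximum drusen size (measured by total volume of drusen) and number of intermediate or large drusen", by arm, visit and eye, with absolute values, change and percentage change. The listing instruction repeats the name without the parenthesis: "All maximum drusen size and number of intermediate or large drusen results will be listed for the ITT set".

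The protocol adds little. The row in Table 1 (Section 5.2.1) reads "Change in drusen from baseline", and no sub-items can be read in the text available for this review. Section 10.6 says that the retinal images "will be transmitted to a central reading center for evaluation", but defines neither a size nor a volume measure. Addendum Section 1 says that its analyses "do not supersede or replace any previously specified analyses, unless specified otherwise".

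**The concern.** The endpoint's name and its stated measure do not describe the same thing. Maximum size is a property of one lesion, the largest. Total volume is a sum, so it rises when further small drusen appear even if the largest is unchanged or smaller, and falls when small drusen regress even if the largest grows. If the rule is followed as written, the tables present a burden measure under the name of a largest-lesion measure. At stake is what may be concluded about the largest druse from the change and percentage change in those tables, including the direction.

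**Working it through.** The plan gives no drusen figure to reproduce, so the check has two parts.

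**1. The definitions side by side.**

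| Place | What it gives |
|---|---|
| Main SAP 2.2.4 | Endpoint name: maximum drusen size. No metric (diameter, area or volume) stated |
| Addendum 6.7.22, summary | Same name, measured by total volume |
| Addendum 6.7.22, listing | Same name, no mention of volume |
| Protocol 10.6 | Central reading of the images; no metric |
| Addendum 15 | Eight changes listed, none about drusen |

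Nothing in the documents defines maximum size through volume or justifies volume as a stand-in for it.

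**2. Can the two quantities disagree in direction?** For drusen with diameters d₁, …, dₙ in one eye, let M = max(dᵢ) and V = c·Σdᵢᵏ. Take k = 3 for lesions of equal shape and k = 2 for lesions of constant height. The constant c cancels in percentage change. The number of lesions n enters V but not M.

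All diameters below are assumptions, in µm.

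*Eye A.* Baseline: one of 200 and five of 100. Follow-up: one of 180 and eight of 130.
- M: 180/200 = 0.90, a fall of 10%.
- V, k = 3: baseline 200³ + 5·100³ = 13,000,000; follow-up 180³ + 8·130³ = 23,408,000; ratio 1.80, a rise of 80%.
- V, k = 2: baseline 200² + 5·100² = 90,000; follow-up 180² + 8·130² = 167,600; ratio 1.86, a rise of 86%.

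*Eye B.* Baseline: one of 200 and ten of 120. Follow-up: one of 220 and three of 120.
- M: 220/200 = 1.10, a rise of 10%.
- V, k = 3: baseline 200³ + 10·120³ = 25,280,000; follow-up 220³ + 3·120³ = 15,832,000; ratio 0.63, a fall of 37%.
- V, k = 2: baseline 200² + 10·120² = 184,000; follow-up 220² + 3·120² = 91,600; ratio 0.50, a fall of 50%.

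Main SAP 2.2.4 does not say that size means diameter, so I repeated the first line of each eye with other metrics for the largest druse. In Eye A the change is −10% in diameter, −19% in area (0.90² = 0.81) and −27% in volume (0.90³ = 0.729). In Eye B it is +10%, +21% (1.10² = 1.21) and +33% (1.10³ = 1.331). The disagreement in direction holds for all three metrics and for both shape assumptions.

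**The case against.** The strongest reply is that the addendum discloses its measure. The sentence that names the variable also says that it is a volume, so a reader of Section 6.7.22 is not deceived, and the lesion count is reported alongside. Table and listing specifications are in a separate document, and the standardized imaging protocol mentioned in Protocol 10.6 is not available here; either may settle the derivation. Total volume is also not spelled out as a sum over the whole eye, so the volume of the largest druse cannot be strictly excluded.

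Much of this stands as a limit on the point, but it does not remove it. Disclosing a measure does not make it measure the named quantity, and the listing sentence drops the disclosure. Reading total volume as the volume of one lesion is not the plain meaning; if it was intended, the wording needs correcting anyway.

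Two stronger inferences are tempting and not supported. First, a reader might infer that the reported direction will be wrong. The examples are constructed and the documents contain no drusen data, so they show that disagreement can happen, not how often. Second, a reader might infer from Addendum Section 15 that an established derivation was replaced without notice. The main SAP has no drusen derivation to replace, and Section 15 is visibly incomplete: the uACR summary in Section 6.7.23 is not listed there either. Because the protocol row's sub-items cannot be read here, a conflict with the protocol cannot be shown.

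**Conclusion.** The point holds as a mismatch between the endpoint named in main SAP 2.2.4 and the variable specified in Addendum 6.7.22. Followed as written, the rule reports a different quantity from the one named, so this is more than missing detail. It rests on the plain reading that total volume sums over drusen and that maximum refers to the largest one. It does not depend on whether size means diameter, area or volume.

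Its size in this trial cannot be estimated; the percentages above are illustrations only. The reach is small. The endpoint is exploratory and its summary descriptive, and Addendum 6.2 plans no formal testing of open-label data. The eye examination is optional and confined to chosen sites, with follow-up only for participants who had drusen before pegcetacoplan. The primary and secondary results, type I error and power are untouched.

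**What to change.** First establish what the central reading center graded.

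- If it graded a largest-druse size per eye, report that as maximum drusen size, in the metric it used, and report *total drusen volume* as a separately named variable.
- If it graded only volume, rename the variable *total drusen volume* in Section 6.7.22, the summaries and the listings. Record the departure from main SAP 2.2.4 in Addendum Section 15, and draw no conclusion about maximum drusen size.

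In either case, state in Section 6.7.22 whether the volume is summed over the eye or over a defined region. The second route costs wording and relabelling only. The first adds a summary row from values already graded. Neither calls for new patient assessments.

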6.7.23. The Change from Baseline in uACR

The observed values for urine albumin-to-creatinine ratio (uACR), measured by triplicate first-morning spot urine or 24-hour urine collection, will be summarized separately by treatment group and visit based on the ITT Set by using available data through the Week 52 assessment. Summaries will present the descriptive statistics for baseline, absolute values, change and percentage change from baseline data by visit. The baseline derivation of FMU uACR will be based on the same logic as described for FMU uPCR.

7. SAFETY ANALYSIS

7.1. Adverse Events

Further detail is provided in the main SAP Section 7.1. The same summaries for RCP as in the main SAP will be repeated for OLP (except for rejection episodes and graft loss where only descriptive summaries are required at Week 52) using all available data through the Week 52 assessment.

Besides the AESI summaries as per the CRF form checkbox question "Is this event an AESI?", additional summaries for the AEs of special search will be provided based on the special search teams provided by Apellis safety team, more specifically:

- Infections: SOC-infections and infestations; HLGT- Bacterial infectious disorders, HLGT- Fungal infectious disorders, HLGT- Viral infectious disorders
- Hypersensitivity: SMQ-Hypersensitivity (narrow)
- Acute Kidney Injury: SMQ- Acute Renal Failure (narrow)
- Thrombocytopenia: HLT- Thrombocytopenias, PT-Platelet count decreased, PT-Plateletcrit decreased, PT-Platelet count abnormal

AEs will be summarized by treatment groups and period. Data will be presented in 5 columns: (1) Pegcetacoplan group's RCP results; (2) Pegcetacoplan group's OLP results; (3) Placebo group's OLP results; (4) OLP results combined (in other words, combining columns 2 and 3); (5) for all results since Pegcetacoplan injection (in other words, combining columns 1 and 4). The classification of AEs in the RCP or OLP will be based on the AE start date compared to the RCP/OLP threshold as defined in the main SAP Section 13.3.

For AE summaries that relate to rejection episodes, in addition to the preferred terms specified in the main SAP, one additional preferred term of "Transplant rejection" is also added based on Apellis team review.

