An overall summary for TEAEs, including number of participants who experience a TEAE, number of total TEAEs, and number of unique TEAEs, will be provided:

- TEAE
- Treatment-related TEAE
- Infusion-related TEAEs
- Serious TEAE
- Maximum severity of TEAEs
- Infusion site reaction
- TEAE leading to treatment withdrawn
- TEAE leading to dose interruption
- TEAE leading to study discontinuation
- TEAE leading to death
- Rejection episodes (for posttransplant only, based on PTs of "KIDNEY TRANSPLANT REJECTION", "RENAL AND PANCREAS TRANSPLANT REJECTION", "MULTIPLE ORGAN TRANSPLANT REJECTION", "SOLID ORGAN TRANSPLANT REJECTION")
- Graft loss (for posttransplant only, based on PTs of "TRANSPLANT FAILURE",
 "ENGRAFT FAILURE", "RENAL TRANSPLANT FAILURE", "REMOVAL OF
 RENAL TRANSPLANT", "GRAFT LOSS")

The following summaries will be provided:

- TEAEs by SOC and PT
- TEAEs by PT in decreasing order of frequency
- Treatment-related TEAEs by SOC and PT
- Infusion-related TEAEs by SOC and PT
- Serious TEAEs by SOC and PT
- TEAE by SOC, PT and maximum severity
- TEAE leading to treatment discontinuation by SOC and PT
- TEAE leading to dose interruption by SOC and PT
- TEAE leading to study discontinuation by SOC and PT
- TEAE leading to death by SOC and PT
- Treatment-emergent adverse events of special interest (AESIs) by SOC and PT
- Serious treatment-emergent AESIs by SOC and PT
- Exposure-adjusted incidence TEAEs by SOC and PT
- Exposure-adjusted incidence serious TEAEs by SOC and PT

Exposure-adjusted incidence rate of an AE is defined as the number of events divided by the total duration of exposure of the participants at risk during treatment, which is computed as following:

Exposure-adjusted incidence rate = n*100/EY,

where n is the number of participants impacted; the exposure year (EY) = (sum of time to onset of the event)/365.25, where time to onset of the event = date of onset of event – Day 1 date +1. For participants without the event, time to onset is censored as follows: time to onset of the event = (last dose date + 56 days) – Day 1 date +1. For participants who experienced the same event on multiple occasions: time to onset of the event = date of onset at the first occasion – Day 1 date +1.

The following listings will be provided:

- All AEs
- Serious adverse events (SAEs)
- AEs leading to study drug discontinuation
- Death
- Treatment-related adverse events
- Infusion-related adverse events

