13.2. Definition of Study Days

Unless otherwise noted, study days of an evaluation are defined as number of days relative to the first dose date of study drug, which is designated as day 1, and the preceding day is day -1, the day before that is day -2, etc.

- For assessments on/after study day 1, study days are calculated as:
 - (date of assessment– date of study day 1 + 1)
- For assessments before study day 1, study days are calculated as:
 - (date of assessment date of study day 1)

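### Exposure-adjusted adverse event rates by period pair period-specific events with exposure counted from Day 1; as written, the open-label rates come out about 43–46% too low for uncommon events

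*SAP*

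**What the plan says.** Main SAP Section 7.1 lists "Exposure-adjusted incidence TEAEs by SOC and PT" and a matching table for serious events. The rate is "Exposure-adjusted incidence rate = n*100/EY", and the denominator is described as "the total duration of exposure of the participants at risk during treatment". For a participant with the event the text reads "where time to onset of the event = date of onset of event – Day 1 date +1". For a participant without it, "time to onset of the event = (last dose date + 56 days) – Day 1 date +1". Main SAP Section 13.2 counts study days "relative to the first dose date of study drug, which is designated as day 1". Protocol Section 9.1 says that study drug in the RCP may be placebo, so Day 1 for a placebo participant is the first placebo dose.

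Addendum Section 7.1 carries these tables forward: "The same summaries for RCP as in the main SAP will be repeated for OLP". It shows five columns: (1) pegcetacoplan group in the RCP, (2) pegcetacoplan group in the OLP, (3) placebo group in the OLP, (4) columns 2 and 3 together, and (5) everything after the first pegcetacoplan dose. Each event goes to a period by its start date, using the boundary in main SAP Section 13.3: the OLP starts at the first OLP dose and the RCP ends the day before. No exposure start or end is given for any column. Addendum Section 13 redefines baseline for the OLP set but not Day 1 or exposure years. Addendum Section 1 says that earlier analyses stand unless the addendum specifies otherwise.

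**The concern.** A rate needs events and person-time from the same window. Here the events are cut at the OLP boundary and the person-time is not. Nobody can have an OLP-onset event before the OLP starts, yet the stated formula counts roughly 26 to 28 earlier weeks for every participant in columns 2 to 4. For former placebo participants that is placebo time. For the pegcetacoplan group it is earlier active treatment, which is still not time at risk of an OLP-onset event. Column 5 is meant to begin at pegcetacoplan, but it takes in the same placebo time for the switchers. Column 1 has the mirror problem, because nothing stops its exposure at the OLP start.

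Of the adverse event summaries listed in main SAP 7.1, only these two tables adjust for differing exposure. Column 5 needs that adjustment most, since it combines up to 52 weeks of pegcetacoplan in one group with about 26 weeks in the other.

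**Working it through.** The documents give no open-label exposure total or rate, so there is no planned figure to reproduce. The check applies the main SAP 7.1 formula directly.

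**Inputs**
- Last dose on day 364, the end of two 26-week treatment periods (main SAP 3.1).
- A 56-day tail (main SAP 7.1).
- OLP start on day 182 (week 26) for adolescents without a biopsy, and as late as day 196 (week 28) for participants who have the week 26 biopsy (Protocol 6.1.3 and Table 2).

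**Columns 2 to 4, event-free participant**
- As written: (364 + 56) − 1 + 1 = 420 days.
- From OLP start on day 182: 420 − 182 + 1 = 239 days; 239/420 = 0.569, so 43.1% too low.
- From OLP start on day 196: 420 − 196 + 1 = 225 days; 225/420 = 0.536, so 46.4% too low.

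Event-free participants dominate the denominator when events are uncommon. Participants with events make the gap wider: an onset on OLP day 28 after a start on day 182 counts as 182 + 28 − 1 = 209 days instead of 28.

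**By OLP incidence**
This assumes a constant hazard over an OLP risk time T of 239 or 225 days, with λ = −ln(1 − p)/T. Mean OLP time is p/λ, and the time as written adds (OLP start − 1) days.

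| Incidence p | Too low, start day 182 | Too low, start day 196 |
|---|---|---|
| 1% | 43.2% | 46.6% |
| 10% | 44.4% | 47.7% |
| 25% | 46.6% | 49.9% |
| 50% | 51.2% | 54.6% |

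At 10% and a day 182 start, the rate is 16.1 per 100 exposure years with an OLP clock and 9.0 as written.

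**By last dose date, event-free participant**
- Stopping on day 273: 55.0% to 59.3% too low.
- Dosing to about day 455 (assumed, from the extension of roughly 3 months allowed in some countries by Protocol Appendix 2): 35.4% to 38.2% too low.

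**Column 5, equal arms, all entering the OLP**
- Start day 182: (420 + 239)/2 = 329.5 days; 329.5/420 = 0.785, so 21.5% too low.
- Start day 196: (420 + 225)/2 = 322.5 days; 322.5/420 = 0.768, so 23.2% too low.

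**Column 1, event-free participant who continues into the OLP**
Events can count for 181 or 195 days (Day 1 to the day before OLP start).
- No cut at OLP start: 420 days counted; 181/420 = 0.431 and 195/420 = 0.464 of the true rate.
- Last dose read as the last RCP dose, taken as the day before OLP start: 181 + 56 = 237 or 195 + 56 = 251 days counted; 181/237 = 0.764 and 195/251 = 0.777.
- Cut at OLP start: no shortfall.

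**Apparent change from column 1 to column 2 under a constant hazard**
- Column 1 not cut: 239/181 = 1.32 and 225/195 = 1.15, so the OLP looks 15% to 32% higher.
- Column 1 ending at last RCP dose plus 56 days: 0.569/0.764 = 0.745 and 0.536/0.777 = 0.690, so the OLP looks about 25% to 31% lower.
- Column 1 cut at OLP start: the OLP looks 43% to 46% lower.

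**The case against.** The strongest reply is that this is an omission and not a stated rule. The addendum never says that the OLP clock starts at Day 1. Its tables are by period, column 5 is headed by the start of pegcetacoplan, the denominator is described as time at risk, and Addendum 5.6 uses the same repeat-for-OLP shorthand for drug exposure, where only a period-specific quantity makes sense. A sensible programmer might reset the clock. That stands as far as it goes: the Day 1 clock arrives by reference. But the only formula in force runs from Day 1, Addendum 1 leaves it in force unless changed, and Addendum 13 shows that a reset was written down where one was wanted, for baseline. Two competent programmers could produce OLP rates that differ almost twofold.

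A reader might go further and infer that a constant hazard on pegcetacoplan would look nearly halved in the OLP, a falsely reassuring trend. The documents do not support that. It reads column 2 literally and takes column 1 as correct, although the same formula governs both. With column 1 also read literally, the OLP rate looks higher, not lower.

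Three limits also stand:
- Both periods are planned at 26 weeks, so the crude tables for columns 1 to 3 are broadly comparable and are unaffected.
- The OLP tables are descriptive; Addendum 6.2 plans no formal testing of OLP data.
- The 239 and 225 days include the 56-day tail, which may not be observed in this study for participants who roll into the extension (Protocol 6.1.4). Without the tail on either side, the shortfall is 49.7% (183/364) to 53.6% (169/364).

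**Conclusion.** The mismatch is real and worth correcting. It follows from applying the main SAP formula to the addendum's period columns. The 43–46% shortfall in columns 2 to 4 holds for uncommon events, a last dose on day 364 and an OLP start between days 182 and 196. It grows with incidence and with early stopping, and shrinks with extended dosing. The 22–23% shortfall in column 5 rests on equal arms and full entry into the OLP, neither of which the documents report as an outcome. Column 1 is understated too unless its exposure is cut at the OLP start. The level of the OLP rates is therefore wrong as written, but the direction of an RCP-to-OLP comparison cannot be stated until column 1 is defined. Counts and percentages of participants with events are not touched.

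**What to change.** Add to Addendum Section 7.1 a definition of exposure for each column of the two exposure-adjusted tables:
- Column 1: from Day 1, censored on the day before the first OLP dose, or at last dose plus 56 days for a participant who does not enter the OLP.
- Columns 2 to 4: from the participant's first OLP dose.
- Column 5: from the participant's first pegcetacoplan dose, which is Day 1 for the pegcetacoplan group and the first OLP dose for the placebo group.
- All columns: time to the first onset within the column, measured from that same start date.

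The cost is a few lines of text and a change of reference and censoring dates in the table program. No new data are needed, since the OLP start date is already derived under main SAP 13.3.
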